### **6.1.2 Study Days**

#### **Study Days (Days Relative to the First Dose of Study Drug)**

Study days are calculated for each time point relative to the first dose of study drug. Study days are negative values when the time point of interest is prior to the first study drug dose day. Study days are positive values when the time point of interest is after the first study drug dose day. There is no Study Day 0. Study Day 1 is the day of the first dose of study drug.

#### **Study Drug End Days (Days Relative to the Last Dose of Study Drug)**

Study drug end days are calculated for each time point relative to the last dose of study drug. The last day of study drug dosing is defined as Study Drug End Day 0. Days before it have negative study drug end days and days after it have positive study drug end days.

#### **Final Treatment Value**

The final treatment value is defined as the last non-missing measurement collected after Study Day 1 and on or before Study Drug End Day 2.

#### **Final Post-Treatment Value**

The final post-treatment value for each subject is the last non-missing measurement collected after Study Drug End Day 2 and on or before Study Drug End Day 999.

### **6.2 Definition of Analysis Windows**

For efficacy analyses of HCV RNA, the time windows specified in [Table 1](#) and [Table 2](#) describe how efficacy data are assigned to protocol-specified time points during the Treatment and Post-Treatment Periods, respectively. All time points and corresponding time windows are defined based on the date/time of blood sample collection.

For safety laboratory data, PRO data, Child Pugh score and vital sign data, the time windows specified in [Table 1](#) and [Table 3](#) describe how data are assigned to protocol-specified time points.

If more than one assessment is included in a time window, the assessment closest (except in analyses of SVR) to the nominal time will be used. If there are two observations equally distant to the nominal time, the latest one will be used in analyses. For analyses of SVR (e.g., SVR12), the last value in the window will be used.

If multiple measurements are made on the same day for a safety laboratory parameter or a vital sign parameter, the average of the values will be used to calculate descriptive statistics and in analyses of the mean change from baseline. For summaries of shifts from baseline and potentially clinically significant values, multiple values on the same day will not be averaged; all values will be considered for these analyses.

**Table 1. Analysis Time Windows for HCV RNA and Resistance Endpoints, Safety Laboratory and Vital Sign Measurements, Child Pugh Scores and PRO Instruments (Treatment Period)**

Scheduled Visit	Nominal Day (Study Day)	Time Window (Study Day Range)
Day 1/Baseline a	1	≤ 1 a
Week 4	28	2 to 42
Week 8	56	43 to 70
Week 12 b,c	84	71 to 98
Week 16 c	112	99 to 126
Final Treatment Visit d	2 to ≤ 2 days after last dose of study drug	

a. Day of first dose of study drug.

b. For 12-week and 16-week treatment duration only.

c. For 16-week treatment duration only.

d. The last value within the window will be used to define the Final Treatment Visit value. The upper bound of this Final window is Study Drug End Day 2. Study Drug End Day 0 is defined as the day of the last dose of study drug.

Note: For all windows, data must be on or before Study Drug End Day 2. The result closest to the scheduled time point will be used. PRO instruments are collected at Day 1, Week 4, Week 12 (Arm C only) and End of Treatment Visit, which can be at Week 8, 12 or 16 depending on treatment assignment, or Premature Discontinuation Visit.

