**Table 2. Analysis Time Windows for HCV RNA and Resistance Endpoints (Post-Treatment Period)**

Scheduled Visit a	Nominal Day (Study Drug End Day)	Time Window (Study Drug End Day Range)
Post-Treatment Week 4	28	3 to 56
Post-Treatment Week 12	84	57 to 126
Post-Treatment Week 24	168	127 to 999
SVR 4 b	28	3 to 56
SVR 12 b	84	57 to 126
SVR 24 b	168	127 to 210

a. Post-Treatment Visits are applicable for subjects who received at least one dose of study drug.

b. For SVR windows, the last value in the window will be used.

Note: The result closest to the scheduled time point will be used, except for SVR4, SVR12, and SVR24. For all windows, data must occur after Study Drug End Day 2. Study Drug End Day 0 is defined as the day of the last dose of study drug.

**Table 3. Analysis Time Windows for Safety Laboratory and Vital Sign Measurements, Child Pugh Scores and PRO Instruments (Post-Treatment Period)**

Scheduled Visit a	Nominal Day (Study Drug End Day)	Time Window (Study Drug End Day Range)
Post-Treatment Week 4	28	3 to 56
Post-Treatment Week 12	84	57 to 126
Post-Treatment Week 24	168	127 to 999
Final Post-Treatment Visit b	> 2 days after last dose of study drug	

a. Post-Treatment Visits are applicable for subjects who received at least one dose of study drug.

b. The last value within the Post-Treatment Period window will be used to define the Final Post-Treatment visit value. The lower bound of this Final window is Study Drug End Day 3. Study Drug End Day 0 is defined as the day of the last dose of study drug.

Note: The result closest to the scheduled time point will be used. For all windows, data must occur after Study Drug End Day 2. Vital signs are collected at every post-treatment visit; hematology, chemistry and coagulation panels are collected at PTW4 or PT D/C (if subject discontinued prior to PTW4). PRO instruments and Child Pugh Scores are collected at PTW12 and PTW24 (or PT D/C).

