## **10.9 Patient Reported Outcomes**

The Kidney Disease Quality of Life (KDQOL36™) instruments will be used to collect patient reported outcomes (PROs). The KDQOL-36 is a disease specific Quality of Life instrument to be used in patients with chronic kidney disease. The KDQOL-36 consists of 4 subscales aimed at quantifying both general health and disease specific attributes. The subscales include: the Short Form-12 (a general health subscale SF-12), burden of kidney disease, symptoms/problems, and effects of kidney disease. The results of the SF-12 instrument are summarized into the Physical Component Summary (PCS) score and the Mental Component Summary (MCS) score. The raw scores are transformed linearly to a range of 0 to 100, with higher scores indicating better health-related Quality of Life.

Summary statistics for each protocol-specified visit (number of non-missing observations, mean) and for change from baseline to each protocol-specified, post-baseline visit

(number of non-missing observations, mean, standard deviation, minimum, maximum) will be provided for the KDQOL-36 subscale scores (SF-12 summarized by PCS and MCS, burden of kidney disease, symptoms/problems, and effects of kidney disease).

If a subject starts another treatment for HCV, then all PRO values for this subject measured on or after the start date of the new HCV treatment will be excluded from analyses.

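### End-of-treatment and discontinuation KDQOL-36 questionnaires completed 3 or more days after the last dose are windowed out of the treatment period and relabelled Post-Treatment Week 4 (minor)

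*SAP*

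**What the plan says.** Section 6.2 sets the assignment rule: "For safety laboratory data, PRO data, Child Pugh score and vital sign data, the time windows specified in" Tables 1 and 3 apply. PROs have no window of their own and are not assigned by visit label.

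- **Upper limit on treatment.** The Table 1 note states: "For all windows, data must be on or before Study Drug End Day 2". Footnote d repeats this for the Final Treatment Visit: "The upper bound of this Final window is Study Drug End Day 2". Section 6.1.2 defines the final treatment value as "the last non-missing measurement collected after Study Day 1 and on or before Study Drug End Day 2".
- **On-treatment PRO schedule.** The same note states: "PRO instruments are collected at Day 1, Week 4, Week 12 (Arm C only) and End of Treatment Visit". It adds that this visit is at Week 8, 12 or 16 by assignment, or is the Premature Discontinuation Visit.
- **Post-treatment windows.** Table 3 names PRO instruments in its title. It assigns Study Drug End Days 3 to 56 to Post-Treatment Week 4 (PTW4), 57 to 126 to PTW12 and 127 to 999 to PTW24.
- **Post-treatment PRO schedule.** The Table 3 note states: "PRO instruments and Child Pugh Scores are collected at PTW12 and PTW24 (or PT D/C". PTW4 is not listed.
- **Analysis.** Section 10.9 plans: "Summary statistics for each protocol-specified visit (number of non-missing observations, mean) and for change from baseline to each protocol-specified, post-baseline visit". It does not say whether the end-of-treatment PRO is shown by week or as a Final Treatment Visit.

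**The concern.** The plan schedules a questionnaire at the end of treatment. If it is completed 3 or more days after the last dose, the windowing rule then removes it from the time point it was collected for. The PTW4 window suits vital signs, taken at every post-treatment visit, and the laboratory panels, taken at PTW4. It does not suit an instrument whose next scheduled visit is PTW12.

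In Arms A and B, Week 4 and EOT are the only scheduled on-treatment PRO assessments after baseline, so the EOT value is half of what is planned there. A subject who stops early is plausibly less likely to be seen within 2 days of the last dose than one who finishes on schedule. If so, the values that leave the end-of-treatment summary come disproportionately from subjects who did not complete treatment.

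**Working it through.** The plan states no figure on this point, so there is none to reproduce. The check applies the window rules to example dates.

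**Inputs from the SAP.** The day of last dose is Study Drug End Day 0 (Section 6.1.2). Table 1 ranges in study days are Week 4 = 2 to 42, Week 8 = 43 to 70, Week 12 = 71 to 98 and Week 16 = 99 to 126. All are subject to End Day ≤ 2. Table 3 ranges are those given above.

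**Assumed dates.** Last dose falls on Study Day 56 (Arm A), 84 (Arm B) or 112 (Arm C) for completers. Early stops are placed on Day 20 (Arm A) and Day 50 (Arm B).

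**Formula.** Study day of the questionnaire = last-dose day + End Day. Apply Table 1 if End Day ≤ 2, otherwise Table 3.

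| Case | End Day 2 | End Day 3 | End Day 14 | End Day 57 |
|---|---|---|---|---|
| Arm A, last dose 56 | Day 58: Week 8 and Final Treatment | Day 59: PTW4 | Day 70: PTW4 | Day 113: PTW12 |
| Arm B, last dose 84 | Day 86: Week 12 and Final Treatment | Day 87: PTW4 | Day 98: PTW4 | Day 141: PTW12 |
| Arm C, last dose 112 | Day 114: Week 16 and Final Treatment | Day 115: PTW4 | Day 126: PTW4 | Day 169: PTW12 |
| Arm A, stop Day 20 | Day 22: Week 4 and Final Treatment | Day 23: PTW4 | Day 34: PTW4 | Day 77: PTW12 |
| Arm B, stop Day 50 | Day 52: Week 8 and Final Treatment | Day 53: PTW4 | Day 64: PTW4 | Day 107: PTW12 |

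End Days 5, 7, 28 and 56 also give PTW4 in all five cases. Every value after End Day 2 is in addition a candidate for the Final Post-Treatment value.

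The cut-off, not the week range, does the excluding. For the Arm A completer, Study Days 59 to 70 (70 − 59 + 1 = 12 days, End Days 3 to 14) lie inside the Week 8 range of 43 to 70 but are barred.

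**What Section 10.9 would then show:**

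1. *Summary at the Final Treatment Visit.* The rule takes the last value up to End Day 2. With the EOT questionnaire barred, an earlier one becomes the Final Treatment value. For the Arm A completer seen on Day 59, that is the Week 4 questionnaire. The subject stays in the denominator with an earlier measurement shown as end of treatment. Only a subject with no earlier on-treatment PRO drops out, such as the Day 20 stopper who has none before the discontinuation visit.
2. *Summary by week.* The value enters no weekly row, and the subject has no EOT value.
3. *Either way,* a PTW4 PRO row, if printed, mixes late EOT and discontinuation questionnaires with any PT D/C questionnaires from days 3 to 56.

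Sections 6.3 and 10.9 contain no exception. Their PRO rules cover only missing items and exclusion after a new HCV treatment starts.

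**The case against.** The End Day 2 limit is a deliberate convention, applied uniformly to separate on-treatment from off-treatment data. A questionnaire completed on End Day 3 or later is indeed off drug, and Table 3 gives it a row, so it is not discarded. PTW4 is also not empty of planned PROs, because a PT D/C assessment can fall there. PROs are neither a primary nor a secondary endpoint, and their analysis is descriptive.

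All of this stands, and it limits the point. It does not explain why an assessment planned for the end of treatment should be reported at a post-treatment week with no scheduled PRO visit, or why a Week 4 value should stand in for it.

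Two stronger readings are tempting, and the SAP supports neither:

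- **That a calculable share of 120 end-of-treatment values is lost and a confidence interval widens.** Section 10.9 plans no PRO interval. No weekly row holds all 120 EOT values, because EOT falls at Week 8, 12 or 16 by arm. Under the Final Treatment definition, most late values would be substituted rather than missing. The SAP gives no rate of late visits.
- **That PROs should be taken out of the PTW4 row.** That would leave PT D/C questionnaires on days 3 to 56, which come from study drop-outs, without any window.

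**Conclusion.** The point holds as a minor defect in the windowing rule. For an affected subject the effect is certain: an EOT or discontinuation KDQOL-36 on End Day 3 to 56 is reported as PTW4, and from Day 57 as PTW12. The end-of-treatment result then uses an earlier value or none, depending on a choice that Section 10.9 leaves open.

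The size across the trial cannot be derived. Under the Final Treatment reading, the shift in the mean equals the fraction of subjects with a substituted value times the mean difference between the substituted and the actual EOT score. The SAP gives neither quantity. It also gives no EOT visit window; if nearly all EOT visits occur by End Day 2, few completers are affected. That early stoppers are the most exposed is a plausible assumption, not a documented fact.

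SVR12, the secondary virologic endpoints and the safety analyses are unaffected.

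**What to change.** Add to Section 6.2 that, for PRO instruments only, the assessment collected at the End of Treatment or Premature Discontinuation Visit is assigned to the end-of-treatment (Final Treatment) time point by its recorded visit. Require that it precede any post-treatment visit and any new HCV treatment, and state that it is not also counted at PTW4. State in Section 10.9 that the end-of-treatment PRO is summarised at that time point.

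Keep the Table 3 windows for PT D/C questionnaires. Leave the End Day 2 limit unchanged for HCV RNA, laboratory and vital sign data.

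The cost is a sentence or two of text and a small programming change. The downside is that some end-of-treatment PROs will have been completed a few days or more off drug; a listing that flags those after End Day 2, with the day, makes this visible. A fixed day limit is not needed, and the SAP offers no basis for choosing one.

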## 10.7 Additional Efficacy Analyses

The following additional efficacy endpoints will be summarized for the ITT population:

- The percentage of subjects with HCV RNA  $< LLOQ$  at each post-baseline visit in the Treatment Period (using data as observed);
- The percentage of subjects with SVR4;
- The percentage of subjects with SVR24;
- The percentage of subjects who relapsed after achieving SVR12 (**Relapse24**).
- The percentage of subjects with virologic failure through Post-Treatment Week 12 (i.e., the SVR12 non-responders due to on-treatment virologic failure or Relapse12)

The number and percentage of subjects meeting each additional efficacy endpoint will be calculated along with a two-sided 95% CI using the Wilson's score method. Imputations for missing data will be performed as described in Section 6.3 for analysis of SVR,

virologic failure, and relapse. The first bulleted endpoint above will be presented using data as observed.

A summary of the subjects who completed treatment and relapsed (defined as **Relapseoverall**) will be prepared displaying the number of subjects relapsing overall and by SVR visit window (within the SVR4, SVR12, SVR24 windows or after SVR24 window), including the subject number and the SVR visit window corresponding to the first HCV RNA value of those indicating the occurrence of relapse. A similar summary will be prepared for subjects who prematurely discontinued treatment and relapsed after having HCV RNA < LLOQ at their Final Treatment Visit. A listing of subjects in the ITT population excluded from the relapse denominator (e.g., study drug duration < 52 days for subjects assigned to 8 weeks of treatment) will be provided, as applicable.

A listing of subject numbers and reasons for non-response to SVR12 will be prepared. A similar summary and listing will be prepared for subjects who do not achieve SVR24 (as defined in Section 10.1).

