## **11.0 Safety Analysis**

### **11.1 General Considerations**

Safety analyses will be performed using the safety population. Data will be summarized overall (across all arms).

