### 11.3.2 Statistical Methods

The baseline value for clinical laboratory tests will be the last non-missing measurement on or before the day of the first dose of study drug. Values on Day 1 must also be before

the time of first dose if time is available. The same baseline value will be used for changes at Treatment Period visits and changes at Post-Treatment Period visits.

Changes from baseline to each post-baseline visit, including applicable post-treatment visits, will be summarized. Each protocol-specified laboratory parameter will be summarized with the sample size, baseline mean; visit mean; and change from baseline mean, standard deviation, minimum, median, and maximum.

Individual changes in the laboratory parameters listed in Section 11.3.1 will be tabulated using shift tables. Laboratory data values will be categorized as low, normal, or high based on normal ranges of the laboratory used for each sample. Shift tables from baselineto minimum value and maximum value during the Treatment Period will be created. For each parameter, the shift tables will cross tabulate the frequency of subjects with baseline values below/within the normal range to maximum above the normal range and with baseline values within/above the normal range to minimum below the normal range.

The laboratory parameters listed in Table 10 will be assigned a toxicity grade of 1, 2, 3, or 4. The number and percentage of subjects with a maximum toxicity grade of 1, 2, 3 or 4 will be tabulated. To be counted, the post-baseline value must have a toxicity grade that is more extreme than the toxicity grade corresponding to the baseline value. For each laboratory parameter in Table 10, the summary will also include the number and percentage of subjects with a maximum of at least grade 3. A listing of all relevant laboratory parameters will be provided for each subject who had an increase to grade 2 or higher for any laboratory variable in Table 10.

For CKD 3B and 4 subjects at screening, laboratory calculated eGFR by MDRD at Screening, EOT, and Post Treatment Week 4 will be summarized by mean, sd, minimum, maximum, median and interquartile range as well as by a box-plot.

CKD categorization at EOT is defined according to eGFR and requirement of dialysis in Table 4. For CKD 3B and 4 subjects at screening, number and percentage of subjects

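### On-treatment by-visit summaries of PROs, laboratory values, vital signs and HCV RNA pool the arms although the contributing arms change by visit (from Week 8 for PROs, from Week 12 for the rest), so apparent changes partly reflect who is measured

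*SAP*

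**What the plan says.** **Schedule.** SAP 4.2 treats Arm A (no cirrhosis) for 8 weeks, Arm B (compensated cirrhosis) for 12, and Arm C (treatment-experienced genotype 3) for 16. Section 6.2 assigns HCV RNA, laboratory, vital-sign and PRO data to visits through the study-day windows of Table 1, and on-treatment data must fall no later than two days after the last dose. The Week 8 row has no restriction by duration. The Week 12 row carries footnote b ("For 12-week and 16-week treatment duration only") and footnote c ("For 16-week treatment duration only"). The Week 16 row carries footnote c alone.

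**PROs.** The note to Table 1 says that "PRO instruments are collected at Day 1, Week 4, Week 12 (Arm C only) and End of Treatment Visit", the last of these being a visit "which can be at Week 8, 12 or 16 depending on treatment assignment, or Premature Discontinuation Visit".

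**Summaries.**
- 10.9 (PROs): "Summary statistics for each protocol-specified visit", and change from baseline.
- 11.3.2 (laboratory): "Changes from baseline to each post-baseline visit, including applicable post-treatment visits, will be summarized". 11.4.2 plans the same for vital signs.
- 10.7 (HCV RNA below LLOQ): a percentage "at each post-baseline visit in the Treatment Period (using data as observed").

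None of these names a split by arm. For safety, 11.1 says "Data will be summarized overall (across all arms"), and 5.1.3 agrees. For efficacy, 5.1.1 combines Arms A, B and C. Yet 4.1 sets the objective of assessing safety by treatment duration and cirrhosis status.

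**The concern.** A reader takes a by-visit table as a course over time on drug. Here the set of subjects changes between columns by design, not through dropout, and the arms are defined by features that plausibly bear on the outcomes: cirrhosis, genotype and prior treatment. A step between columns then mixes any real change over time with a change in who is measured.

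The mixing is greatest for PROs. On the Table 1 windows, no subject on the scheduled visits contributes at both Week 8 and Week 12, and the Week 12 column joins end-of-treatment scores from Arm B with mid-treatment scores from Arm C. For laboratory values, vital signs and HCV RNA the composition first changes at Week 12.

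At stake is the reading of quality of life, laboratory, vital-sign and viral-suppression tables in the study report, and whether the pooled safety tables deliver what 4.1 promises.

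**Working it through.** **The plan's own figure.** Section 4.3 gives a half-width of 0.031 for an SVR12 rate of 97% in 120 subjects. Check: 1.96 × √(0.97 × 0.03 / 120) = 0.0305, which agrees after rounding. The present point does not depend on it.

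**Which arms fill each on-treatment visit** (4.2, Table 1 and its note; scheduled visits only, since premature-discontinuation visits fall wherever they occur):

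| Visit | Laboratory, vital signs, HCV RNA | PRO |
|---|---|---|
| Week 4 | A, B, C | A, B, C |
| Week 8 | A, B, C | A (end of treatment) |
| Week 12 | B, C | B (end of treatment), C (mid-treatment) |
| Week 16 | C | C (end of treatment) |
| Final Treatment Visit | A, B, C | A, B, C |

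**Coverage.** The SAP gives 120 subjects and a cap of about 30 with compensated cirrhosis, but no arm sizes. Assumed: Arm B 15 to 30, Arm C 2 to 20, the rest in Arm A, no dropout.
- PRO Week 8: 120 − B − C = 70 to 103 subjects, 58% to 86%.
- Week 12, all data types: B + C = 17 to 50 subjects, 14% to 42%.
- Week 16, all data types: C = 2 to 20 subjects, 2% to 17%.

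**What pooling can produce.** Assume arm means of 0 (A), −3 (B) and −6 (C) that never change, with sizes 85, 30 and 5. These are illustrative values, not estimates. The pooled mean is the sum of n × mean over the arms present, divided by the total n.
- Week 4: (85×0 + 30×(−3) + 5×(−6)) / 120 = −120/120 = −1.0.
- Week 8, laboratory: the same arms, so −1.0. Week 8, PRO: Arm A only, so 0.
- Week 12: (30×(−3) + 5×(−6)) / 35 = −120/35 = −3.4.
- Week 16: −6.

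The pooled PRO series is −1.0, 0, −3.4, −6 and the laboratory series is −1.0, −1.0, −3.4, −6, although no arm moves. Over the assumed range of arm sizes, Week 12 lies between −3.2 and −4.7. Shown by arm, each series is flat.

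**Which columns are exposed.** If the assumed values are levels, the illustration applies to raw visit means; the within-subject change is then 0 in every arm and the change column is flat. If the values are mean changes from baseline that differ by arm, it applies to the change column too. The as-observed HCV RNA percentage has no baseline correction at all.

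**Consistency with the rest of the SAP.** Section 11.2.2 tabulates adverse events by system organ class and preferred term by arm and overall, and 11.3.2 shows CKD-stage change by arm. An arm split is therefore already in use.

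**The case against.** **These are descriptive tables.** No hypothesis is tested (4.3, 10.2), and no comparison across visits is planned. This stands and limits the weight of the point.

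**The main safety readouts do not use by-visit means.** Toxicity grades, laboratory shifts, hepatic criteria and potentially clinically significant vital signs rest on on-treatment extremes or on any qualifying value; eGFR is summarized at screening, end of treatment and Post-Treatment Week 4. This also stands.

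**There are partial safeguards.** Change from baseline removes fixed level differences between arms, and laboratory and PRO tables show the number of observations. But differences in change remain, 11.4.2 lists no sample size, and a falling n does not show what each arm did.

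**PROs may be meant differently.** Section 10.9 speaks of protocol-specified visits, and the Table 1 note names end of treatment as one visit. On that reading all arms share it, and Week 12 belongs to Arm C. This is a fair reading, but 6.2 also routes PRO data through the day windows, so the text leaves both open. A reader should not conclude that a Week 8 PRO table from Arm A alone is certain to be produced.

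**Stronger inferences that the document does not support.**
- That Week 8 is also a single-arm visit for laboratory, vital-sign and HCV RNA data: Table 1 leaves that row open to all durations.
- That the full Arm A versus Arm B difference appears between the Week 8 and Week 12 PRO columns: Week 12 also holds Arm C. In the illustration that difference is 3.0 and the step is 3.4.
- That footnotes b and c are a substantive contradiction: b suits laboratory, vital-sign and HCV RNA data and c suits the Arm C PRO visit, so this is probably a labelling slip.

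**Conclusion.** The point holds. Composition changes from Week 12 for laboratory values, vital signs and HCV RNA, and already at Week 8 for PROs if the Table 1 windows are applied as written. Pooled changes across these visits partly reflect who is measured. A reader might infer that they reflect nothing else; the document does not support that, because it gives no outcome difference between arms and does not exclude real change over time.

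The coverage figures rest on assumed arm sizes and no dropout. The size of any distortion cannot be derived from the SAP; the illustration shows only how it arises.

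Separately, pooled laboratory and vital-sign tables do not meet the objective in 4.1 of assessing safety by treatment duration and cirrhosis status.

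The primary SVR12 analysis is unaffected, and the Final Treatment Visit and post-treatment visits are scheduled for every arm. The change should be made, but it is not critical to the trial's main conclusion.

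**What to change.** 1. In 10.7, 11.3.2 and 11.4.2, present Weeks 12 and 16 by treatment arm. Keep pooled on-treatment summaries only at Week 4, Week 8 and the Final Treatment Visit.
2. In 10.9, analyse the end-of-treatment PRO assessment as the Final Treatment Visit and report Week 12 as an Arm C visit. Pool PROs on treatment only at Week 4 and the Final Treatment Visit. If PRO tables by Week 8, 12 and 16 are kept, show them by arm.
3. Amend 11.1 and 5.1.3 to allow the arm split, in line with 4.1. Arm C is not defined by cirrhosis status, so an arm split meets that objective largely but not completely.
4. In Table 1, label footnotes b and c on the Week 12 row by data type.

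Pooled post-treatment summaries can stay. The cost is SAP wording and extra columns in planned tables; no new data are needed. The drawback is small Arm C cells (2 to 20 subjects under the assumptions above). Pooling hides these at Week 12 and does not avoid them at Week 16, where Arm C is the only arm scheduled.
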